11.2 Disposition of Patients

Screened patients are defined as any patient who signed informed consent.

Randomized patients are defined as all patients, with a signed informed consent, randomized via the IXRS.

The number and percentage of patients screened, randomized, and included in the analyses, and those who complete the study, will be presented by treatment group. The number and percentage

of randomized patients who withdraw prior to completion, and the primary reason for withdrawal, will be summarized by treatment group.

Study completion information will be presented by patient in a data listing. A by-patient listing of patients who are screen failures, and the reason for screen failure, will also be presented.

11.2.1 Analysis Populations

The primary efficacy analysis population will be the intent-to-treat (ITT) population, which consists of all randomized patients. All patients will be analyzed according to the treatment to which they are randomized.

The safety population will include all randomized patients who have received at least one dose of the study drug. All patients will be analyzed according to the treatment they have actually received.

The pharmacokinetic population will be a subset of the safety population and include subjects with evaluable pharmacokinetics data.

11.3 Statistical Methods

11.3.1 Study Drug Exposure and Compliance

The extent of study treatment exposure and compliance will be summarized for the safety population. The duration of study drug exposure is defined as [last dose date – first dose date + 1 day] regardless of unplanned intermittent discontinuations. Treatment compliance is defined as the number of infusions received compared to the scheduled number of infusions. Treatment compliance, the number of infusion interruptions, and the percentage of subjects with compliance <80% will be summarized.

11.3.2 Analyses of Efficacy Endpoints

11.3.2.1 Analysis of dystrophin protein level

A primary objective of this Phase 2/3 study is to evaluate the efficacy of WVE-210201 by assessing changes in dystrophin protein levels. Therefore, the primary efficacy endpoint for the United States and Other regions, as applicable, and the key secondary endpoint for the EU and Japan is the change in dystrophin protein level (% normal) from baseline. The treatment policy estimand, which assesses the effect of treatment initially assigned at baseline (regardless of adherence to the planned course of treatment), will be used. The analysis population will be the ITT population. The main estimator is a Bayesian analysis of covariance (ANCOVA). The model will include fixed effects for mean change from baseline in dystrophin levels at each time point for placebo and fixed effects for the increase or decrease in dystrophin compared to placebo for each treatment arm at each time point.

Let the change from baseline in dystrophin level at time point j for patient i be Y_{ij} , for $j = 1, 2, 3$ and $i = 1, \dots, n$. Time periods $j = 1, 2$, and 3 , refer to the post-baseline visits at 12, 22 and 46 weeks; each patient will have one Y_{ij} with either $j = 1, 2$, or 3 . The ANCOVA model is

$$Y_{ij} = \alpha_j + \theta_{t(i),j} + \epsilon_{ij};$$

$$\epsilon_{ij} \sim N(0, \sigma_{t(i),j}^2).$$

The $\alpha_j, j = 1, 2, 3$, parameters represent the mean change from baseline in dystrophin level at each time point for placebo-treated patients. For patient i , the treatment arm is labelled $t(i)$ with 0 for placebo, 1 for WVE-210201 3 mg/kg and 2 for WVE-210201 4.5 mg/kg. The effect of treatment T at time j is the parameter $\theta_{T,j}, T = 0, 1, 2$ and $j = 1, 2, 3$. For placebo, the effect is assumed to be 0 ($\theta_{0,j} = 0$). Thus, the treatment effect parameter for treatment T at time j represents the mean difference in the change from baseline in dystrophin at time j compared to placebo. The errors for the individual observations, ϵ_{ij} , are assumed independent and follow a normal distribution. The standard deviation, $\sigma_{T,j}, T = 0, 1, 2$ and $j = 1, 2, 3$, is specific to treatment arm and visit.

Summaries of the posterior distribution for the treatment difference in dystrophin compared to placebo at each time point for each arm will be provided including the probability that each treatment is superior to placebo at each time point, $\Pr(\theta_{T,j} > 0)$, as well as mean and 95% credible intervals.

The dystrophin analysis will be supplemented with dystrophin data from the ongoing Open-label extension study to the Phase 1 trial (WVE-DMDX51-002). These results will be available at the time of the first dystrophin interim analysis.

Missing dystrophin data can result from intercurrent events which include discontinuation of the study and non-evaluable biopsies. Previous pivotal studies in DMD, including exon skipping therapies, have had low study discontinuation rates (e.g. 0.6% and 2.7%) so it is anticipated that missing data resulting from study discontinuation will be limited (^{57,58}). With the selected estimand, missing dystrophin results due to study discontinuation will be handled using baseline imputation. Non-evaluable dystrophin will be addressed using imputation under the assumption of missing-at-random (MAR). The regression method for monotone missing data will be used for the multiple imputation with baseline dystrophin as a covariate and imputation stratified by treatment arm.

There will be two interim dystrophin efficacy analyses and a final dystrophin efficacy analysis. The dystrophin treatment effects will be declared significant at the interim or final analyses using a gatekeeping strategy where the WVE-210201 4.5 mg/kg arm is assessed first and, if significant, the WVE-210201 3 mg/kg arm is assessed. To account for the three possible analyses of the dystrophin treatment effects, a Bonferroni-level adjustment will be applied. A one-sided, significance threshold of $1 - (0.025/3) = 0.991667$ will be used for the Bayesian posterior probability of superiority of each dose compared to placebo. If successful for WVE-

210210 4.5 mg/kg, the same threshold will be used for WVE-210210 3 mg/kg. Specifically, success will be declared for WVE-210201 4.5 mg/kg if

1. $\Pr(\theta_{2,1} > 0) > 0.991667$ at the first dystrophin interim analysis,
2. $\Pr(\theta_{2,2} > 0) > 0.991667$ at the second dystrophin interim analysis, or
3. $\Pr(\theta_{2,3} > 0) > 0.991667$ at the final dystrophin analysis.

With this plan, the 12-week WVE-210201 4.5 mg/kg treatment effect is assessed at the first dystrophin interim analysis, the 22-week WVE-210201 4.5 mg/kg treatment effect is tested at the second dystrophin interim analysis and the 46-week WVE-210201 4.5 mg/kg treatment effect is tested at the final dystrophin interim analysis. Similar comparisons will be made for the WVE-210201 3 mg/kg treatment effect if the 4.5 mg/kg treatment effect is significant.

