11.3.2.2 Analysis of North Star Ambulatory Assessment (NSAA)

Another primary objective is to evaluate the efficacy of WVE-210201 by assessing changes in the NSAA. Therefore, the primary efficacy endpoint for the EU and Japan and the key secondary endpoint for the United States and Other regions is the change in NSAA from baseline over 48 weeks. The treatment policy estimand which assesses the effect of treatment initially assigned at baseline (regardless of adherence to the planned course of treatment) will be used. The analysis population will be the ITT population. The main estimator will be a Bayesian progression model (BPM) to compare the change in NSAA between patients treated with WVE-210201 and placebo treated patients^{59,60}. The placebo data from this study will be augmented with historical control data via a Bayesian meta-analytic approach.

The BPM assumes a non-parametric rate of progression of the NSAA for placebo patients and a proportional rate of slowing NSAA progression for the treated patients relative to the placebo patients at each time point. The model will include covariate effects to measure differences in the rates of progression based on patient-specific baseline covariates. Additionally, random patient variability will be accounted for using patient-level random effects of the rate of NSAA progression. Borrowing from historical control data to augment the placebo arm information will entail including a random data source effect to model the between-source variability in NSAA progression rates.

The NSAA analysis will be independent of the dystrophin analysis described in [Section 11.3.2.1](#). Let the NSAA at visit j for patient i be Y_{ij} , for $j = 0, \dots, 4$ and $i = 1, \dots, n$. The Y_{i0} observation corresponds to the baseline visit. Visits $j = 1, 2, 3, 4$ refer to the post-baseline visits (each separated by 12 weeks). Let X_i be a vector of dimension C of baseline covariates for patient i that have been standardized. The DPM is

$$Y_{ij} = \gamma_i + \exp(\theta_{t(i)} + \eta_i + \alpha X_i + \delta_{s(i)}) \sum_{k=0:j} \beta_k + \epsilon_{ij}; \\ \epsilon_{ij} \sim N(0, \sigma_{t(i),s(i)}^2).$$

Patient-specific random effects, $\gamma_i, i = 1, \dots, n$, represent the patient-specific mean NSAA at the time of randomization.

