11.5.1 Dystrophin Interim Analyses

Interim analyses of dystrophin will determine if efficacy is demonstrated prior to study conclusion and may allow for stopping randomization to the WVE-210201 3 mg/kg arm. The

first interim dystrophin analysis will compare dystrophin protein levels between WVE-210201 and placebo using the Week 12 open biopsies collected from up to the first 30 patients randomized. The second interim dystrophin analysis will compare dystrophin protein levels between WVE-210201 and placebo from approximately 40 patients with Week 22 open biopsies (collected from the 31st through 70th patient). The dystrophin interim analyses will be supplemented with dystrophin data from the ongoing OL extension study to the Phase 1 trial (WVE-DMDX51-002). A final analysis of dystrophin will occur when up to 80 patients (collected from the 71st through a maximum of the 150th patient) have Week 46 open biopsies. The significance thresholds for the dystrophin analyses are described in [Section 11.3.2.1](#). If the first or second interim dystrophin analysis results in a significant WVE-210201 treatment effect, randomized patients will continue to complete 48 weeks of follow-up to assess clinical outcomes and other endpoints.

Randomization to the WVE-210201 3 mg/kg treatment arm may be stopped based on the interim analysis of dystrophin. Specifically, randomization to the WVE-210201 3 mg/kg treatment arm will stop, if there is a high posterior probability that the high dose is effective, and the low dose is less efficacious of the high dose. The specific thresholds are included in the SAP.

If randomization to the 3 mg/kg treatment arm is stopped, patients originally randomized to the 3 mg/kg treatment arm will be transitioned to the WVE-210201 4.5 mg/kg treatment arm and all future patients will be randomized to WVE-210201 4.5 mg/kg or placebo at a 2:1 ratio. For clinical endpoint analyses, including the NSAA, patients originally randomized to the WVE-210201 3 mg/kg arm who transition to the WVE-210201 4.5 mg/kg treatment arm will not be included in WVE-210201 4.5 mg/kg treatment effect estimation.

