11.5.2 NSAA Interim Analyses

In addition to comparing dystrophin levels between the WVE-210201 and placebo treatment arms, there will be interim analyses for NSAA sample size re-estimation at 4 pre-specified enrollment targets. The enrollment targets are included in the DMC charter and SAP. A final NSAA analysis will take place when all randomized patients have been followed for 48 weeks. The purpose of these interim analyses is to potentially stop enrollment based on the predicted success of the 48-week NSAA analysis assuming the current trial sample size.

The predictive probability of success (PPS_{NSAA}) for 48-week NSAA given the current enrollment will be estimated at each NSAA interim analysis and based on the posterior probability that the estimated DRR, $\exp(\theta_T)$, is less than or equal to a target DRR. If the DRR meets a threshold, enrollment will stop as the probability of NSAA success is high enough not to warrant additional randomization of patients. All enrolled patients will continue in the study until completion. The target DRR and the specific thresholds are included in the SAP. If none of the thresholds are reached, the sample size of 150 will be enrolled.

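### The dystrophin model called ANCOVA has no covariate: adding baseline dystrophin and age group is a cheap improvement, and the role of the open-label extension data needs one clarifying sentence

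*Combined protocol and SAP*

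**What the plan says.** **The model.** Section 11.3.2.1 labels the dystrophin model a Bayesian ANCOVA in the ITT population. The equation gives change from baseline as a week mean for placebo, plus an arm-by-week effect, plus an error whose SD depends on arm and week. The verbal description lists the same terms. Baseline dystrophin is a covariate only in the multiple imputation of non-evaluable biopsies. Section 6.1.1 stratifies randomisation by age (up to 9 years, over 9 years). It exempts the 12-patient Japanese PK cohort from that factor and places later Japanese patients in strata of their own.

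**The extension data.** Section 11.3.2.1 states: "The dystrophin analysis will be supplemented with dystrophin data from the ongoing Open-label extension study to the Phase 1 trial (WVE-DMDX51-002". It continues: "These results will be available at the time of the first dystrophin interim analysis". Section 11.5.1 limits the statement to the interims: "The dystrophin interim analyses will be supplemented with dystrophin data from the ongoing OL extension study to the Phase 1 trial". Neither section gives a prior, weight, source term, number of patients, dose or biopsy week.

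**What depends on the model.** Success for 4.5 mg/kg is a posterior probability above 0.991667 at any of three analyses, with 3 mg/kg tested next. Section 11.5.1 adds: "Randomization to the WVE-210201 3 mg/kg treatment arm may be stopped based on the interim analysis of dystrophin". On the criteria for this it says: "The specific thresholds are included in the SAP".

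**The concern.** An ANCOVA adjusts for covariates, and this one has none. Visit and arm are design factors, and taking change from baseline as the outcome is not the same as adjusting for baseline. Baseline dystrophin must be measured in any case to form the outcome, and age is recorded. Leaving both out may discard precision where it is scarcest: the first interim has up to 30 patients, about 10 per arm once the two placebo groups are combined, and section 4.1.2 says a positive interim may support early registration in some regions.

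The extension sentence raises a different question. If those patients entered the posterior probability, they would have no concurrent placebo, and section 5.2 would have barred them from this trial because of prior WVE-210201 treatment. The type I error would then depend on how far they differ from the randomised patients for reasons other than drug. Section 11.3.3 cites simulations but does not say whether these covered external data.

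**Working it through.** **1. The plan's own figures.** Section 11.1 assumes 150 patients, 10% dropout, a difference of 4.0, an SD of 3.0 and two-sided 5%. Evaluable patients: 150 x 0.9 = 135, or 45 per arm for one dose against combined placebo. The exact t-test gives power above 99.99%, so the stated figure of more than 99% reproduces. The threshold 1 - 0.025/3 = 0.991667 also reproduces.

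**2. Power at the first look.** The tests are week-specific. At the first interim, with 10 against 10 and the same difference and SD assumed at Week 12, a one-sided t-test at 0.00833 has 64% power. A posterior with arm-specific SDs and flat priors gives about 56%. Precision has practical value at this look.

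**3. Precision from adding the covariates.** Let k be baseline SD divided by post-baseline SD, and r the correlation of baseline with post-baseline. Neither is in the documents; k = 0.3 or 1 and r = 0.3 to 0.7 are assumed. Age group is counted as a cost with no gain.

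- Variance ratio, adjusted to unadjusted: (1 - r²)/(1 + k² - 2rk).
- Cost of estimating two terms: x (1 + 2/24) at 30 patients and 3 arms; x (1 + 2/138) at 150 patients and 9 arm-by-week cells.
- Precision change: 1/(product) - 1.

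| k | r | Variance ratio | 30 patients | 150 patients, common slopes |
|---|---|---|---|---|
| 0.3 | 0.3 | 1.000 | -8% | -1% |
| 0.3 | 0.5 | 0.949 | -3% | +4% |
| 0.3 | 0.7 | 0.761 | +21% | +30% |
| 1 | 0.3 | 0.650 | +42% | +52% |
| 1 | 0.5 | 0.750 | +23% | +31% |
| 1 | 0.7 | 0.850 | +9% | +16% |

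The loss arises when r = k, because baseline is then unrelated to change and only the cost of the extra terms remains. A simulation of the 30-patient case gave -8.3% to +43.4%.

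**4. Extension data, hypothetical pooling.** The looks use different patients. With randomised patients only, the error for 4.5 mg/kg dystrophin over three looks is 1 - (1 - 0.00833)³ = 2.48% by the normal formula, and 1.8% by simulation with arm-specific SDs. Now assume that 10 extension patients at full weight join the 4.5 mg/kg Week 12 cell, with SD 3 and no drug effect. A non-drug shift of +1 point moves the arm mean by 1 x 10/20 = 0.5. The standard error is 3 x sqrt(1/10 + 1/20) = 1.162. The first-look error is 1 - Φ(2.394 - 0.5/1.162) = 2.48%, and the total is 1 - (1 - 0.0248)(1 - 0.00833)² = 4.1% (3.0% by simulation). At shifts of -1, 0 and +0.5 the totals are 1.9%, 2.5% and 3.1% (1.5%, 2.0% and 2.4% by simulation). At half weight and +1 the total is 3.0% by the normal formula.

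**5. Power without the extension data.** Success may come at any look. Suppose enrolment stopped at an assumed 100 patients, leaving about 10, 13 and 10 per arm at the three looks, with a 4-point effect at each. By t-test: 1 - (1 - 0.636)(1 - 0.788)(1 - 0.636) = 97%. With the arm-specific-SD posterior (about 56%, 74% and 56%): 1 - 0.44 x 0.26 x 0.44 = 95%. On the posterior basis, raising the first look to 74% with 10 fully exchangeable extension patients gives 1 - 0.26 x 0.26 x 0.44 = 97%.

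**The case against.** **On the covariates.** The unadjusted randomised comparison is valid, so this can be called a matter of preference. The largest gain also needs a generous assumption. With an SD of change of 3, k = 1 and r = 0.3 imply a baseline SD of 3/sqrt(1.4) = 2.5 points, which looks large beside the 0.93% average level that section 1.1 reports in eteplirsen-treated patients. At k = 0.3 the first interim gains only when r is high. All of this stands: it limits the expected gain but does not remove the mismatch between label and equation.

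**On the extension data.** A reader might infer that extension patients are pooled into the randomised cells and that the type I error therefore exceeds 2.5%. The documents do not support this. The population is all randomised patients, and the model has no source term. Section 11.5.1 identifies the biopsies for each analysis: the first 30 randomised patients, the 31st to 70th, then "A final analysis of dystrophin will occur when up to 80 patients", from the 71st onward, have Week 46 biopsies. Where the plan intends borrowing it says so: "The placebo data from this study will be augmented with historical control data via a Bayesian meta-analytic approach", with a data source effect. What remains is that an analysis being supplemented can also mean that data join it, and that the two sections differ on whether the final analysis is touched.

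Two further inferences fail. Reporting the data alongside does not by itself show 2.5% control for the whole family in section 11.3.3, which also includes NSAA; the 2.48% covers 4.5 mg/kg dystrophin only. Nor would leaving the extension data out make the trial depend on the final look. Section 11.5.2 does allow a smaller trial ("The purpose of these interim analyses is to potentially stop enrollment based on the predicted success of the 48-week NSAA analysis"), but three-look power for 4 points stays at about 95-97% at an assumed 100 patients.

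**Conclusion.** The model lacks the covariates that its name implies, and adding them is a cheap improvement. The effect is on precision only. The stated range rests on the assumed k and r, and its lower end is a small loss at the first interim if baseline is weakly related to change.

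The extension sentence is an undefined term, not a demonstrated error. Reporting alongside is the better-supported reading, and the method may be in the SAP text that was not available. Inflation requires both pooling and a positive non-drug shift. The figures of 2.5% at no shift and 4.1% at +1 point are hypothetical, because the number, dose, week, weight and shift are all assumed, and +1 is large beside 0.93%.

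**What to change.** 1. In section 11.3.2.1, add baseline dystrophin and age group (up to 9, over 9 years) as fixed effects, with slopes common to arms and biopsy weeks. Take age group from recorded age, since the Japanese PK cohort was not stratified by age. Consider a Japan/non-Japan term at the final analysis, because Japanese patients are randomised in separate strata.

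2. State that the three success probabilities and the criterion for stopping 3 mg/kg randomisation use only patients randomised in this study, with extension dystrophin as supportive. Align sections 11.3.2.1 and 11.5.1 on whether the final analysis is touched. If borrowing is intended, give the number, dose and biopsy week of the extension patients, add a source term or discount as in the NSAA model, and report type I error under drift, for example from -1 to +1 point.

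The cost is wording and two model terms, with no new data. The Bonferroni threshold can stay, since it does not need independent looks. Precision could fall by up to about 8% at the first interim. If pooling had been intended, dropping it would lower first-interim power for 4 points from about 74% (10 exchangeable patients) to 56%, but three-look power by only about 2 percentage points in the 100-patient case.

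### The imputation model for non-evaluable biopsies does not name biopsy week, although the dystrophin analysis model is specific to arm and week

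*Combined protocol and SAP*

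**What the plan says.** Section 4.1.2 schedules the second biopsy at Week 12 for the first 30 patients, at Week 22 for the next 40 and at Week 46 for the rest. Section 11.5.1 puts the last group at up to 80. Every patient therefore contributes a single post-baseline dystrophin value.

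The analysis model in Section 11.3.2.1 is specific to the week. Placebo enters through "fixed effects for mean change from baseline in dystrophin levels at each time point for placebo". Each dose then has its own departure from placebo at every week, and the standard deviation "is specific to treatment arm and visit". The Week 12 effect is tested at the first interim, the Week 22 effect at the second and the Week 46 effect at the final analysis. By-week posterior summaries are promised for each arm.

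The same section treats two kinds of missing value differently. For patients who leave the study, "missing dystrophin results due to study discontinuation will be handled using baseline imputation". Non-evaluable biopsies are imputed under missing-at-random. The procedure is regression-based multiple imputation for a monotone pattern, specified "with baseline dystrophin as a covariate and imputation stratified by treatment arm". Nothing else is named as a covariate or stratum.

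**The concern.** An imputation model should contain at least the factors on which the analysis model depends. Here the analysis separates the three weeks and the listed imputation terms do not. Someone who programs the sentence as written would fit one regression per arm across all weeks. A missing Week 46 value would then be centred near the arm's average over Weeks 12, 22 and 46, and the same holds for a missing Week 12 or Week 22 value. The imputed values would also share one residual variance per arm, whereas the analysis model lets the variance differ by week.

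The estimates exposed are the Week 46 effect at the final look, the Week 22 effect at the second interim, and the by-week summaries reported at the end. Dystrophin is the primary endpoint for the United States and other regions and a key secondary endpoint for the EU and Japan.

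**Working it through.** **Inputs from the documents**
- Biopsy cohorts of 30, 40 and up to 80 patients (Sections 4.1.2 and 11.5.1).
- Allocation 1:1:2:2. With the two placebo groups combined, as in the analysis model, one third of patients fall in each of placebo, 3 mg/kg and 4.5 mg/kg. That gives about 10, 13.3 and 26.7 per arm at Weeks 12, 22 and 46.
- Week 46 difference 4.0% of normal, SD 3.0%, dropout 10% (Section 11.1).

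**Assumptions, because the documents give no figure**
- Active-arm means at Weeks 12 and 22; several profiles are tried.
- Non-evaluable rates of 5%, 10% and 20%, equal across weeks.
- No change over time on placebo, so imputed placebo values do not shift.

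**The plan's own figure.** 150 × 0.9 = 135 patients, or 45 per arm. The standard error is 3.0 × √(2/45) = 0.63, and 4.0/0.63 = 6.3. Power for one dose against placebo exceeds 99.99%, so the stated figure of more than 99% reproduces. It supplies the effect and SD used here but does not address imputation.

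**Formulas**
- Pooled arm mean = Σ (week weight × week mean), with weights 30/150 = 0.20, 40/150 = 0.27 and 80/150 = 0.53.
- Shift of an imputed value = pooled mean − true week mean.
- Bias in the week's effect = non-evaluable share × shift.

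**Example with means 1/2/4.** Pooled mean = (10 × 1 + 13.33 × 2 + 26.67 × 4)/50 = 2.87.
- Week 46: 2.87 − 4 = −1.13; bias −0.06, −0.11 and −0.23 at 5%, 10% and 20%.
- Week 12: 2.87 − 1 = +1.87; bias +0.09, +0.19 and +0.37.
- Second interim, with only Week 12 and Week 22 biopsies: pooled mean (10 × 1 + 13.33 × 2)/23.33 = 1.57. The Week 22 shift is −0.43 and the bias at 10% is −0.04.

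**Other profiles, final analysis**

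| Assumed means, Weeks 12/22/46 | Shift of imputed value | Bias at 10% non-evaluable |
|---|---|---|
| 1.04/1.91/4 (linear rise) | +1.81/+0.94/−1.15 | +0.18/+0.09/−0.11 |
| 1/2/4 | +1.87/+0.87/−1.13 | +0.19/+0.09/−0.11 |
| 3/4/4 (plateau) | +0.80/−0.20/−0.20 | +0.08/−0.02/−0.02 |
| 4/4/4 (flat) | 0/0/0 | 0/0/0 |
| 4/4/3 (late fall) | −0.53/−0.53/+0.47 | −0.05/−0.05/+0.05 |

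**Scale.** With 26.7 per arm, the standard error of the Week 46 difference is 3.0 × √(2/26.7) = 0.82. A bias of 0.11 is 0.14 of that, and under 3% of the 4.0-point effect.

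**Simulation check.** Regression imputation with 10 imputations was run in 600 simulated trials under the linear rise at 10% non-evaluable. Estimated effects at Weeks 12/22/46 were 1.24/2.08/3.86 without biopsy week and 1.05/1.93/3.94 with it, against true values of 1.04/1.91/4.0. The 0.991667 threshold was passed at Week 46 in 98.0% of trials without week and 99.3% with it. Gaps of this size also appear, in both directions, under the flat profile, where there is no bias. They are close to simulation error.

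**The case against.** The strongest reply is that the plan nowhere says the weeks are pooled. The outcome is indexed by week, each look tests one week, and imputing each cohort from itself would fit that structure. The monotone wording does not settle it: a baseline value followed by one outcome is monotone within a single cohort as well as in a combined set. This stands in part. A reader might infer that the plan mandates pooling in contradiction of its own model, and the text does not go that far. Pooling is the literal reading of the listed terms, and imputation within week is not excluded. Section 11.3.2.1 does name its covariate and its stratum, however, and does not refer the choice elsewhere.

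A reader might also infer that Week 46 is always pulled down and Week 12 always pushed up. That needs a response that rises between Weeks 12 and 46. The only time-specific effect given is 4.0% at Week 46. The non-evaluable rate is likewise unstated: the 10% in Section 11.1 is dropout, which is handled by a different rule. Open biopsy was chosen to secure adequate tissue, so the rate may be low.

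Nor should the point be read as distorting the first interim decision. Only Week 12 trial biopsies enter there, so no other week of this trial can be mixed in. How the supplementary open-label extension data would enter the imputation is not stated. Finally, it would be wrong to infer a raised false-positive risk at Week 46 under a rising profile, since the bias then runs toward no effect.

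**Conclusion.** The point holds in a limited form. The written imputation model omits biopsy week and so does not match an analysis model that is specific to arm and week. Followed literally, it biases the by-week effects whenever the active-arm response changes with time.

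The size is small. Under the assumed 1/2/4 profile, the Week 46 bias at the final analysis runs from −0.06 to −0.23 points as the assumed non-evaluable rate goes from 5% to 20%. The Week 12 summary is affected more, both in points and relative to its own mean (+0.09 to +0.37 on an assumed 1%), but no decision is taken on it at that stage. These figures rest on an assumed time course and rate, and the sign changes if the response falls late. The case for changing the text is that the mismatch is easily removed, not that it threatens the trial's conclusion.

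**What to change.** State in Section 11.3.2.1 that the imputation model includes biopsy week as a factor within each treatment arm, together with baseline dystrophin. Imputing separately within each arm and week would also agree with the analysis means and would let the residual variance differ by week. With only about 10 patients per arm at Week 12, the factor version is more stable. The same sentence can say whether the open-label extension data are used in the imputation.

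The cost is one term in the imputation code and one sentence of text. No extra patients, biopsies or visits are needed. It is best settled before the first interim dystrophin results are available.
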